9.5.2 Secondary/Exploratory Outcomes

In both Phase 2 and Phase 3, exploratory outcomes include change in depression, impairment, anxiety, and potential mechanisms of action over time.

Specifically, we will look at change over time the in the following variables. The primary outcome in a subsequent efficacy study is in **bold and underlined**. Secondary outcomes are in standard text. *Potential mechanisms are in italics*.

- **Depression, Adolescent report: change in QIDS from BL to M3;** BL to M6 (phase 3 only), and BL to M9 (phase 3 only)
- Depression, Adolescent report: change in BDI from BL to M3; BL to M6 (phase 3 only), and BL to M9 (phase 3 only)
- Depression, Parent report: change in QIDS from BL to M3; BL to M6 (phase 3 only), and BL to M9 (phase 3 only)
- Depression, Parent report: change in BDI from BL to M3; BL to M6 (phase 3 only), and BL to M9 (phase 3 only)
- Functional impairment, Adolescent report: change in CIS from BL to M3; BL to M6 (phase 3 only), and BL to M9 (phase 3 only)
- Functional impairment, Parent report: change in CIS from BL to M3; BL to M6 (phase 3 only), and BL to M9 (phase 3 only)
- Anxiety, Adolescent report: change in SCARED-R from BL to M3; BL to M6 (phase 3 only), and BL to M9 (phase 3 only)
- Anxiety, Adolescent report: change in SCARED-R from BL to M3; BL to M6 (phase 3 only), and BL to M9 (phase 3 only)
- Sleep Disturbance, Adolescent report: change in PROMIS- Sleep disturbance from BL to M3
- *Mindfulness, Adolescent report: change in subscales of TMS from BL to M3; BL to M6 (phase 3 only), and BL to M9 (phase 3 only)*
- *Self-Compassion, Adolescent report: change in SCS from BL to M3; BL to M6 (phase 3 only), and BL to M9 (phase 3 only)*

9.6 Data Analyses

Qualitative Data Analysis

Focus groups (Phase 1) or interviews (Phase 2, 3) will be recorded and transcribed. We will use a template organizing style to analyze qualitative data [34]. [name] will oversee the process. She will develop an initial codebook with *deductive* codes. *Inductive* codes capturing emergent themes will arise from team-level review of the transcripts. Once the codes are developed, members of the scientific team will independently code remaining transcripts; 20% of transcripts will be double coded and reviewed to ensure coding fidelity. Information gleaned will then be reviewed by the scientific team and used to modify manuals and procedures.

Quantitative Data Analysis

In Phase 2 and Phase 3, we will use descriptive statistics to summarize all variables. We will also conduct exploratory analyses of change over time in depression (which will be the primary outcome in an efficacy study), impairment and anxiety (which will be secondary outcomes) and potential mechanisms of action. All variables will be examined and tested for distributional assumptions prior to statistical analysis. We will use within-subject t-tests, separated by treatment group. In this study, these analyses should be considered exploratory. Any data that violates statistical assumptions will either be transformed accordingly and appropriate statistical tests will be applied (e.g., non-parametric approaches such as the Wilcoxon signed rank test in lieu of t-tests). We will look at outcomes for the entire group of enrolled participants for Phase 2 and Phase 3. In addition, in Phase 3, we will examine outcomes for 2 sets of subgroups:

- c. Study A vs. Study B
- d. Pre-COVID enrollment (including those who participated in some in-person and some video classes, which is the majority of the Pre-COVID enrolled group) vs. Post-COVID enrollment (i.e., those who consented and started video-based classes from the start).

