4. SELECTION AND ENROLLMENT OF PARTICIPANTS

4.1 Inclusion Criteria

Participants must meet all of the relevant inclusion criteria to participate in the study.

Phase 1 (Focus Group) Inclusion Criteria – Adolescents

These are designed to be similar to inclusion criteria for Phase 2 and 3, but because adolescents will not be participating in the yoga intervention and are only attending a single focus group, criteria is more inclusive than Phase 2 and 3 to reduce assessment burden.

- a) Adolescents must have elevated depressive symptoms, defined by a score of 8 or higher on the PHQ-8, and a "1" or greater on at least one of the following two items: sad mood, or

anhedonia.

- b) Adolescents must be aged 13-18.
- c) Adolescents must be medically cleared for moderate physical activity by their primary care physician. This criterion will be assessed by adolescent or parents self-report that the adolescent has a current (dated in the past year) statement from their pediatrician that the adolescent may participate in school or camp programs including physical education.
- d) Adolescents must be able to read and write English sufficient to complete informed consent and engage in interventions.
- e) Adolescents aged 13-17 must assent to be in the study, and their parent/legal guardian must consent to their participation. Adolescents aged 18 must consent to be in the study.
- f) Able to attend a focus group.

Phase 2, Phase 3 Study A, and Phase 3 Study B Inclusion Criteria – Adolescents

Please note, inclusion criteria for Phase 2, Phase 3 Study A, and Phase 3 Study B are identical, with the exception that, for Phase 3/Study B, we will not require elevated depressive symptoms (a) or stable treatment (b).

- a) Adolescents must have elevated depressive symptoms, defined by a score of 10 or higher on the Quick Inventory of Depression –Adolescent Version-- Clinician Rating (QIDS-A-CR; [12-14]), including endorsement of either sad mood or anhedonia on the QIDS.
- b) Other treatment for depression must be stable at baseline. Adolescents do not have to be in other treatment for depression, but, if they are, it must be stable with no substantive changes for the past 8 weeks. If unexpected changes in treatment occur during the study protocol period, participants can remain in the study and this treatment change will be captured as data.
- c) Adolescents must be aged 13-18.

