4.2 Exclusion Criteria

Phase 1 (Focus Group) Exclusion Criteria – Adolescents

- a) Adolescents may not have current suicide ideation or behavior that warrants immediate treatment. They may have passive ideation (i.e., thoughts that life is not worth living), but

may not have active suicide ideation, intent, plan, or an attempt within the previous 6 months. We will not actively assess this for Phase 1, but we will exclude an adolescent if they indicate they have active suicide ideation.

- b) Adolescents cannot currently be engaged in yoga classes, as these are the study interventions.

Phase 2, Phase 3 Study A, and Phase 3 Study B Exclusion Criteria – Adolescents

Exclusion criteria for Phase 2, Phase 3 Study A, and Phase 3 Study B are identical.

- a) QIDS- A-SR may not be higher than a score of 21. This ensures that adolescents are not severely depressed.
- b) Adolescents may not meet criteria for the following:
 - i. Autism spectrum disorder (AS) “cannot be ruled out” (via MINI), and symptoms are of sufficient severity to interfere with study treatment per clinician judgment;
 - ii. Current psychotic disorder
 - iii. Lifetime history of a manic episode
 - iv. Anorexia or Bulimia in past 3 months
 - v. Substance use disorders in past 12 months, and symptoms are of sufficient severity to interfere with study treatment per clinician judgment

These will be assessed with the Mini-International Neuropsychiatric Interview (MINI).

- c) Adolescents may not have current untreated active suicide ideation or behavior. They may not have had a suicide attempt in the previous 6 months. They may not have suicide ideation that is so severe that the study clinician judges it will interfere with study participation (e.g., if the clinician judges they need a higher level of treatment now or potentially very soon). This means that adolescents with active suicide ideation may be included if they are receiving stable mental health services (e.g., therapy, counseling) and suicidal ideation is known to the mental health provider. Adolescents may be included if they have passive ideation (i.e., thoughts that life is not worth living) but are not in active treatment.
- d) Adolescents cannot currently be engaged in yoga classes, as this is the study intervention.
- e) Adolescents cannot be pregnant as yoga should be modified for pregnancy [15].

Parent Exclusion Criteria for all Phases

None. Please see parent inclusion criteria above.

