| Assess feasibility, acceptability, and safety of both the yoga intervention and the comparison group ** This is primary ** | See Table 5 for a complete list (Endpoints examined separately for main participants and study B participants; also examined separately for participants consented pre-COVID and post-COVID) | Descriptive statistics (see Table 5) and qualitative data analysis |
| Assess within-group changes on outcomes. The primary outcome will be depression symptom severity at post-intervention (M3). Secondary outcomes include depression severity at follow-up (9 months), and self-report of depression, functional impairment, anxiety, and sleep at post-intervention (M3) and 9 months. ** This is exploratory ** | Endpoint = post-intervention (M3) (Endpoints examined separately for main participants and study B participants; also examined separately for participants consented pre-COVID and post-COVID) | Within-subjects t-tests (e.g., from pre-intervention to post-intervention/M3). We will conduct analyses separately by treatment group. We will calculate effect sizes (Cohen's d) from pre- to post-treatment/M3, with corresponding confidence intervals. |
| Assess within-group changes on self-compassion and meta-cognitive awareness ** This is exploratory ** | Endpoint = post-intervention (M3) (Endpoints examined separately for main participants and study B participants; also examined separately for participants consented pre-COVID and post-COVID) | Within-subjects t-tests (e.g., from pre-intervention to M3). We will conduct analyses separately by treatment group. |

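### Section 9.6 lets a distribution pretest decide scale and test at about 14 to 17 per arm; fix one raw-scale analysis for every outcome and both arms

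*Combined protocol and SAP*

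**What the plan says.** Section 9.6 (Quantitative Data Analysis) first promises descriptive statistics for all variables. It then sets a data-driven rule: "All variables will be examined and tested for distributional assumptions prior to statistical analysis". For data that fail: "Any data that violates statistical assumptions will either be transformed accordingly and appropriate statistical tests will be applied", with the Wilcoxon signed-rank test as the example. The sentence opens an alternative that it never completes, so the order of transformation and change of test is undefined. The section names no pretest and no threshold. It does not say whether the baseline, the Month 3 score or the change is tested, or whether the arms are pooled for the test. The comparison itself is within arm: "We will use within-subject t-tests, separated by treatment group".

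Table 4 (Section 9.1.1) adds for the clinical outcomes: "We will calculate effect sizes (Cohen's d) from pre- to post-treatment/M3, with corresponding confidence intervals". It gives neither the standardiser nor the scale to be used after a transformation.

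Section 4.1 sets the entry floor for Phase 2 and Study A: "Adolescents must have elevated depressive symptoms, defined by a score of 10 or higher on the Quick Inventory of Depression", clinician-rated version. Study B has no such floor. Section 6.2.2b uses the QIDS-A-CR at the first baseline visit to establish eligibility, and Table 2 lists no later pre-treatment QIDS. The qualifying score is therefore also the baseline outcome value.

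**The concern.** With few participants per arm, a test of distributional shape has little power when the shape is poor and still raises false alarms when it is good. Letting it choose the analysis means that chance partly decides whether an outcome is reported in raw points, on a transformed scale or as a rank test.

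The entry floor adds a specific problem. It cuts the lower tail off the baseline QIDS-A-CR, so that variable can look non-normal by design. A paired t-test needs roughly normal changes, not a normal baseline. Read literally, a rule that tests all variables can move the analysis off the raw scale for a reason that does not affect the t-test.

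What is at stake is planning information. The stated objective is to prepare a fully powered non-inferiority trial, and Section 9.5.2 marks QIDS change from baseline to Month 3 as the primary outcome of a subsequent efficacy study. That trial needs change in raw points with its precision, the Month 3 SD and the baseline to Month 3 correlation.

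**Working it through.** The plan gives no power, alpha, SD, correlation or effect-size figure, so there is none to reproduce. The checks below concern direction and size. QIDS means, SDs and correlations are assumptions throughout.

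**1. Numbers per arm.** Study A enrols 34 (Section 9.2.1). Assuming 1:1 allocation, which fits the even block sizes in Section 9.2.2, 34/2 = 17 per arm. The Month 3 retention target in Table 5 is 80%: 17 × 0.80 = 13.6, about 14.

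**2. How a pretest behaves at that size.** Assume Shapiro-Wilk at 0.05 (6,000 samples per setting). If it is applied by arm and both arms share one distribution with rejection rate p, the arms get different verdicts with probability 2p(1 − p). For gamma shape 2 at n = 14, that is 2 × 0.366 × 0.634 = 0.464.

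| Distribution | p, n = 14 | Arms differ | p, n = 17 | Arms differ |
|---|---|---|---|---|
| Normal | 0.054 | 0.101 | 0.049 | 0.093 |
| Gamma, shape 4 | 0.194 | 0.313 | 0.252 | 0.377 |
| Gamma, shape 2 | 0.366 | 0.464 | 0.450 | 0.495 |
| Exponential | 0.638 | 0.462 | 0.754 | 0.371 |

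Even gamma shape 2 data pass more often than they fail. The columns on arms differing apply only if the pretest is done by arm. If one choice serves both arms, disagreement between arms disappears, but disagreement between outcomes remains.

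**3. The baseline can fail while the change does not.** Simulate bivariate normal scores with SD 4.5 and r = 0.5, rounded to whole points, and keep those with baseline at least 10. At n = 14 the baseline is rejected in about 13 to 38% of samples (untruncated means 14 down to 10) and the change in about 6%. The reason is dilution. In this model the change equals (1 − r) × baseline plus independent normal noise with variance 4.5² × (1 − 0.5²) = 15.2. At an untruncated mean of 10, the baseline SD after selection is about 2.81 (mean change 4.63 divided by baseline-SD d of 1.65). The truncated part then contributes (0.5 × 2.81)² = 1.97, which is 1.97/17.2, or about 11%, of the change variance.

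**4. Cohen's d under the entry floor.** For a normal distribution cut at 9.5 (score 10 or more), with means 8 to 14 and SDs 4 to 5, the baseline SD falls to between 0.54 and 0.82 of its untruncated value. For the same mean change, a baseline-SD d is multiplied by 4/3.27 = 1.22 up to 4/2.15 = 1.86.

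Selection also produces regression to the mean. With SD 4.5, r of 0.5 to 0.7 and means 10 to 14 (1,000,000 draws per setting before selection), zero true change still gives an apparent fall of 0.4 to 1.6 points. Ranges of d:

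| Standardiser | No true change | True 3-point fall |
|---|---|---|
| Baseline SD | 0.11 to 0.58 | 0.95 to 1.65 |
| Average SD | 0.10 to 0.46 | 0.88 to 1.31 |
| Month 3 SD | 0.09 to 0.39 | 0.83 to 1.12 |
| Change SD | 0.11 to 0.39 | 0.85 to 1.20 |

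Without truncation, a 3-point fall gives 3/4.5 = 0.67 for the first three rows and 0.67 to 0.86 for the change SD. Every standardiser is inflated, the baseline SD most. The unstated choice matters within one dataset too: at mean 12 and r = 0.5, the same 3-point fall gives 1.28, 1.10, 0.97 and 0.97 in table order.

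**5. Perspective.** For a change-score d of 0.5, the noncentral-t 95% CI is −0.07 to 1.05 at n = 14 and −0.01 to 1.00 at n = 17. Sampling error is large whatever the definition.

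**The case against.** The strongest reply is that little hangs on this. Table 4 labels within-group change exploratory and feasibility, acceptability and safety primary. Section 9.1 says the trial is not powered for differences or non-inferiority, and no between-arm comparison is planned. Descriptive statistics under Section 9.6 would ordinarily give raw means and SDs, and the correlation can be computed from the same paired data. If the team tests the change scores, step 3 suggests the rule will seldom fire for QIDS. All of this stands and limits the point to an improvement. It does not defend the rule itself: the plan does not say that changes are what is tested, and raw mean change with a CI is not specified.

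Four stronger readings are tempting and are not supported:

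- **Scale and test are chosen separately in each arm.** Only the t-tests are stated to be by arm. A single choice per variable fits the text equally well, so the between-arm figures in step 2 are conditional.
- **Cohen's d is the headline result.** It belongs to an exploratory row of Table 4, and Section 9.5.1 directs primary analyses to feasibility and acceptability.
- **Study A baseline QIDS-A-CR is confined to 10 to 21.** The upper limit in Section 4.2 is on the self-report version: "QIDS- A-SR may not be higher than a score of 21". Only the floor acts directly on the outcome instrument, so step 4 uses the floor alone.
- **Truncation makes the two arms non-comparable.** The entry rule applies equally to both randomised arms, and a switch to the signed-rank test changes the test, not d. Only a transformation used in one arm and carried into d would do that, and none is described. Truncation does hinder comparing d between Study A and Study B, which has no floor.

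It might also be thought that standardising by the Month 3 SD cures the inflation. It reduces it, but regression to the mean remains (0.09 to 0.39 with no true change), and the interventions can themselves alter that SD.

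**Conclusion.** The point holds as a free improvement. The pretest-driven choice in Section 9.6 is an inferior and under-specified method at about 14 to 17 per arm. It can send QIDS results off the raw-point scale because of an entry floor that hardly disturbs the change scores: about 13 to 38% rejection for the baseline against about 6% for the change. Results may then differ in scale or test across outcomes, and across arms only if the pretest is run by arm. The standardiser for d is undefined, and selection on the baseline QIDS inflates pre-post d under any choice.

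These sizes rest on 1:1 allocation, 80% retention, a Shapiro-Wilk test at 0.05, normal underlying scores, and the QIDS means, SDs and correlations assumed above, none of which the documents give except the retention target. The direct truncation concerns the adolescent QIDS-A-CR in Phase 2 and Study A. Other scales are affected only through their correlation with it. The primary aim of the trial is untouched.

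**What to change.** Replace the pretest and fallback sentences in Section 9.6 with one fixed rule for every outcome and both arms:

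- Report mean change in raw points with a t-based (or bootstrap) 95% CI.
- Report the signed-rank test as a prespecified sensitivity analysis, always and not only after a failed pretest. Distributions can still be described, but should not select the analysis.
- Report the Month 3 SD and the baseline to Month 3 correlation from the same participants.
- If Cohen's d stays in Table 4, compute it on the raw scale, name one standardiser and use it in both arms. State that selection on the baseline QIDS-A-CR inflates pre-post d through regression to the mean whichever standardiser is used, most with the baseline SD.

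The cost is a few lines of analysis-plan wording. No new data, visits or participants are needed. The reported d may look less favourable if the named standardiser is not the baseline SD.

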10. DATA COLLECTION AND QUALITY ASSURANCE

10.1 Data Collection Forms

Participants will directly enter self-report data into REDCap, and data collected as part of an interview will be written on a paper CRF and double-entered into REDCap. For the RCT (Phase 3), there will be two REDCap databases – a “blind” database and a “nonblind” database. As described in the assessment table, some assessments are described as being collected by a blind evaluator (research assistant), whereas some are not (because these assessments, by their nature, would break the blind.) There will also be a database that we will use for tracking participants.

Any data, forms, reports, audiorecordings, and other records that leave the site will be identified only by a participant identification number (Study ID, SID) to maintain confidentiality. All paper records will be kept in a locked file cabinet. All data collected will be entered into an electronic database which is stored on a secure server (REDCap) that is backed up on a daily basis. Participant identifying information will be stored in a separate database and will be password protected and stored on a secure server. Care New England’s instance of REDCap has been deemed HIPAA compliant by CNE Information Technology.

10.2 Data Management

All self-report data will be collected via REDCap. Interviews (e.g., MINI, QIDS) have standardized forms which we will use and which will be double-entered into REDCap. Any discrepancies will be resolved by the Project Manager in consultation with the MPIs as needed.

Please see also “Data Handling and Record Keeping” in the DSMP.

10.3 Quality Assurance

10.3.1 Training

All research personnel, including yoga instructors will have formal training in research with human subjects (e.g., CITI training, NIH Human Subjects training). Drs. [name], [name], [name], and [name] will provide training to and supervise research assistants. Research assistants will also have training in Good Clinical Practice. MPIs and [name] will provide training on the MINI and QIDS through didactic teaching, role plays, and feedback on audiotaped sessions. [name] will provide training and supervision to yoga instructors, and CBT group leaders. [name] (our lead yoga instructor) will assist with yoga instructor training and supervision.

10.3.2 Quality Control Committee

Drs. [name], [name], [name], and [name] will be responsible for quality control of this study. They review recruitment and retention reports, and AE reports, on weekly basis.

10.3.3 Metrics

QIDS Reliability

Research assistants will be trained to administer the QIDS and will be considered certified once they rate 5 practice QIDS to a gold standard rating with an ICC of .80 or greater for total scores. Subsequently, [name], [name], or [name] will rate 10% of all QIDS administered. Significant discrepancies (greater than 2 for the total score) will be grounds for re-training.

10.3.4 Protocol Deviations

During weekly study meetings, protocol deviations will be discussed with the MPIs, including plans for corrective action. [name] will also be alerted to deviations as they occur and will alert the MPIs for any deviation requiring immediate action. Protocol deviations will be logged on the protocol deviation tracking sheet and filed in the regulatory binder.

All assessment time points have a window of time for completion. However, typically due to circumstances outside of the control of the research staff, assessments occasionally occur outside of that window. Assessments that occur outside of the recommended window for completion will be considered to be protocol deviations, and will be logged as such.

Protocol deviations will be reported to NCCIH once per year, in the annual review. The SMC will also receive a list of protocol deviations in their interim or annual reports. Per Butler Hospital IRB policy, “major protocol deviations/violations, defined as those which increase risk to participants” will be reported promptly to the IRB and no more than 10 working days after the investigator is aware of the event. Minor protocol deviations do not need to be reported.

